12.0 Procedures Involved*

*12.1 Provide a description of **all research procedures or activities** being performed and when they are performed once a subject is screened and determined to be eligible. Provide as much detail as possible.*

NOTE: This should serve as a blueprint for your study and include enough detail so that another investigator could pick up your protocol and replicate the research. For studies that have multiple or complex visits or procedures, consider the addition of a schedule of events table in in your response.

Response: When the potential participants contact the researchers via email, phone calls, text, research team members will ask for eligibility. If they are eligible, we will ask about available times and places for interview and make an appointment. Participants will be provided with the link for the exiting apps in advance of the interviews and we will ask them to download it before the interview day. Private places, such as an office at the University at Buffalo will be used for in-person interview. Or if the participants prefer, the interviews will occur via Zoom or phone call. Before the interview begins, researchers will explain the purpose of the study and potential risks of participating in this research and obtain consent if the participants are 18 or older than 18 years old. We will obtain parent consent and minor assent if they are younger than 18 years old. We will obtain written consent. We will also ask if we can keep their contact information for five years to ask if they want to participate in future research. After obtaining consent, the researchers will ask participants to complete online survey (10 minutes), and ask participants to complete specific tasks on the app (task test performance test) (e.g., creating a personal profile). Then, the researchers will start interviews. For in-person interviews, we will use audio-recorders and for phone and Zoom interviews, we will use a record function on the Zoom application. Each interview will take about 30 to 60 minutes. Before the participants begin interviews, they will complete the survey (18 question) via phone or computer. After the interview is conducted, the recorded files will be transcribed by transcription services and double checked by the research team. All recorded audio files and transcribed files will be saved in the secure computer. All recordings and transcribed copies will be deleted once all the study procedures, including data analysis and reporting is completed.

12.2 Describe what data will be collected.

NOTE: For studies with multiple data collection points or long-term follow up, consider the addition of a schedule or table in your response.

Response: This study has a one-time data collection point. We will conduct the usability survey and task performance test during the interview meeting. After the survey and task performance test, we will conduct the interviews. The audio recording and the transcripts will be obtained. In addition, the contact information, including name, phone number and email address, if they agree, will be collected to schedule the interviews.

12.3 List any instruments or measurement tools used to collect data (e.g. questionnaire, interview guide, validated instrument, data collection form).

Include copies of these documents with your submission.

Response: This will be semi-structured interview. The basic interview questions that will be used are included in the interview guide (attached). As part of the interview, we will ask participants to conduct specific tasks within the app and the prompt is included in the interview guide file. Further follow-up questions will be used for probing. In addition, we will conduct a brief survey using mHealth App Usability Questionnaire.

12.4 Describe any source records that will be used to collect data about subjects (e.g. school records, electronic medical records).

Response: NA

*12.5 Indicate whether or not **individual** subject results, such as results of investigational diagnostic tests, genetic tests, or incidental findings will be shared with subjects or others (e.g., the subject's primary care physician) and if so, describe how these will be shared.*

Response: Individual subject results will not be shared with subjects or others.

*12.6 Indicate whether or not **study** results will be shared with subjects or others, and if so, describe how these will be shared.*

Response: Study results will be shared via publication. Subjects or others may have access to published findings of the study.

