13.0 Study Timelines*

13.1 Describe the anticipated duration needed to enroll all study subjects.

Response: 12 months

13.2 Describe the duration of an individual subject's participation in the study. Include length of study visits, and overall study follow-up time.

Response: Each participant will spend approximately take 30 to 60 minutes to complete the interview, including 10 minutes consenting process, completing the survey, and task performance test. There is only one interview for each subject.

13.3 Describe the estimated duration for the investigators to complete this study (i.e. all data is collected and all analyses have been completed).

Response: This study is expected to take one year to complete data collection and data analysis.

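### Sections 12.1, 12.2 and 13.2 name the usability questionnaire before the app tasks and nothing places the tasks earlier, so some usability ratings may be given before any use of the app

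*Protocol*

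**What the plan says.** The steps of the session appear in four places in the protocol.

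- Section 12.1, main sequence: "After obtaining consent, the researchers will ask participants to complete online survey (10 minutes), and ask participants to complete specific tasks on the app". The next sentence begins the interview: "Then, the researchers will start interviews". A later sentence in 12.1 adds that the survey has 18 questions and is completed before the interview starts.
- Section 12.2: "We will conduct the usability survey and task performance test during the interview meeting", followed by "After the survey and task performance test, we will conduct the interviews".
- Section 12.3 identifies the survey as the mHealth App Usability Questionnaire and describes the app tasks as belonging to the interview, with the prompt held in the interview guide.
- Section 13.2 gives a session of 30 to 60 minutes, "including 10 minutes consenting process, completing the survey, and task performance test".

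On earlier contact with the app, 12.1 says that participants receive a link and "we will ask them to download it before the interview day". On repeat measurement, 12.2 says "This study has a one-time data collection point".

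**The concern.** A usability questionnaire asks respondents to rate an app, so they need to have used it first. The protocol lists the questionnaire ahead of the tasks that give that experience. Beforehand it asks only for a download, and the text shown neither requires nor records any use. Staff who follow the list may collect ratings from participants who have never used the app.

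The primary objective in section 1.0 is feedback on usability from 30 adolescents, and 19.1 summarises the survey with descriptive statistics. Those summaries could combine ratings made before any use with ratings made after differing amounts of unsupervised use, and the protocol text gives no variable to separate the two. With one data collection point, no rating after the tasks is planned, so analysis could not repair the problem afterwards.

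The template note to 12.1 asks authors to "include enough detail so that another investigator could pick up your protocol and replicate the research". An open order for survey and tasks falls short of that.

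**Working it through.** No formula bears on the order of procedures. The check sets side by side every passage that mentions the survey, the tasks or earlier use of the app.

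| Section | Sequence in the text | What it fixes in time |
|---|---|---|
| 12.1, main sequence | consent, survey, tasks, interview | consent first and interview last; survey and tasks are joined only by a conjunction |
| 12.1, later sentence | survey, interview | survey before interview; silent on the tasks |
| 12.2, first sentence | survey, tasks | both fall within the one meeting |
| 12.2, second sentence | survey, tasks, interview | interview after both |
| 12.3 | tasks, then the questionnaire as a further item | no time order; this is a list of instruments |
| 13.2 | consent, survey, tasks | no time order; this is a list of what the duration covers |

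**Order.** Wherever the steps are listed as a session (12.1, 12.2, 13.2), the survey is named first. No passage places the tasks before the survey in time. The sequence is not an explicit rule either, since the only firm constraint is that the interview follows both.

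**Reading of 12.3.** If the interview there means the whole session, as the phrasing of 12.2 and 13.2 suggests, 12.3 agrees with the other sections. If it means the interview proper, the tasks fall inside a step that 12.1 starts only after the survey, so the survey again comes first. Neither reading puts the tasks ahead.

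**Which survey.** Only one survey is described. Section 12.2 calls it the usability survey and 12.3 names the instrument, so taking the online survey in 12.1 to be that questionnaire is an inference, but a firm one.

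**Earlier use.** The only step before the session is the requested download. How many of the 30 participants will have used the app before the survey is not given; it may be none.

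**Session time.** This check concerns only whether reordering costs time. It reads the 30 to 60 minutes in 13.2 as the whole session.

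- Consent 10 + survey 10 = 20 minutes.
- Left for tasks and interview: 30 − 20 = 10 minutes at the least and 60 − 20 = 40 minutes at the most.

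The total is the same whichever of survey and tasks comes first. Section 12.1 can also be read as giving 30 to 60 minutes to the interview alone. The 10 to 40 minutes would then not apply, but the order would still not change the total.

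**The case against.** The strongest reply is that no wrong order is stated. Sections 12.1 and 12.2 join survey and tasks with a conjunction, 13.2 is a list about duration, and 12.3 mentions the tasks before the questionnaire. Naming order should not count in three sections and be ignored in the fourth. The rule in 12.1 that the survey precedes the interview is compatible with consent, tasks, survey, interview. The survey form and the attached interview guide are not shown, and either might set the order or ask about earlier use. Some participants may well open the app after downloading it. Finally, the study is qualitative, has no hypotheses and takes theme saturation as its endpoint, so only descriptive summaries of a supporting data source are exposed.

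Much of this stands and limits the point. The order is list sequence, not instruction. The unseen forms might settle it. The interviews come after the tasks on any reading and are unaffected.

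It does not remove the point. Section 12.3 lists instruments and sets no sequence, whereas 12.1 is the procedural account that staff would follow, and its natural reading puts the survey first. If staff do not follow it, the order may vary between participants, which also mixes the ratings. Possible earlier use by some participants is part of the difficulty, because it makes exposure uneven.

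**Conclusion.** The point holds as a minor one. The protocol leaves the order of questionnaire and tasks open, and its procedural sections list the questionnaire first. A session run that way can collect usability ratings before any use of the app, with no later rating planned.

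The size cannot be put into numbers, because nothing in the protocol gives the extent of earlier use or its effect on the scores. What is exposed is the descriptive summary of the questionnaire, which bears on the primary objective. The interviews, which are the main data source, are not exposed, and no test depends on the scores.

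The conclusion assumes that the online survey is the usability questionnaire and that the unseen survey form and interview guide do not already fix the order or record earlier use. Confidence is medium for that reason.

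**What to change.** In sections 12.1 and 12.2, state one explicit order: consent, any demographic questions, app tasks, usability questionnaire, interview. Reword 12.3 so that its description of the tasks as belonging to the interview matches that order. Optionally, if the survey form does not already do so, add one question on whether the participant opened the app before the session, for description only.

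The cost is wording changes in three subsections and at most one added question. Existing steps are only reordered, so no visits, staff or participants are added, and reordering itself does not lengthen the session.

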13.0 Study Timelines*

13.1 Describe the anticipated duration needed to enroll all study subjects.

Response: 12 months

13.2 Describe the duration of an individual subject's participation in the study. Include length of study visits, and overall study follow-up time.

Response: Each participant will spend approximately take 30 to 60 minutes to complete the interview, including 10 minutes consenting process, completing the survey, and task performance test. There is only one interview for each subject.

13.3 Describe the estimated duration for the investigators to complete this study (i.e. all data is collected and all analyses have been completed).

Response: This study is expected to take one year to complete data collection and data analysis.

14.0 Setting

14.1 Describe all facilities/sites where you will be conducting research procedures. Include a description of the security and privacy of the facilities (e.g. locked facility, limited access, privacy barriers). Facility, department, and type of room are relevant. Do not abbreviate facility names.

NOTE: Examples of acceptable response may be: "A classroom setting in the Department of Psychology equipped with a computer with relevant survey administration software," "The angiogram suite at Buffalo General Medical

Center, a fully accredited tertiary care institution within New York State with badge access,” or, “Community Center meeting hall.”

Response: Meeting rooms at University at Buffalo will be considered first to meet for participants for an interview upon making an appointment. Available meeting rooms or classrooms of community centers or other places which ensures privacy may be used for data collection. If the participant prefers, virtual interviews, using application, Zoom can be used for an interview. Or phone interviews can be conducted if participants prefer.

14.2 *For research conducted outside of UB and its affiliates, describe:*

- *Site-specific regulations or customs affecting the research*
- *Local scientific and ethical review structure*

NOTE: This question is referring to UB affiliated research taking place outside UB, i.e. research conducted in the community, school-based research, international research, etc. It is not referring to multi-site research. UB affiliated institutions include Kaleida Health, ECMC, and Roswell Park Cancer Institute.

Response:

N/A: This study is not conducted outside of UB or its affiliates.

15.0 Community-Based Participatory Research

15.1 *Describe involvement of the community in the design and conduct of the research.*

NOTE: Community-Based Participatory Research (CBPR) is a collaborative approach to research that equitably involves all partners in the research process and recognizes the unique strengths that each brings. CBPR begins with a research topic of importance to the community, has the aim of combining knowledge with action and achieving social change to improve health outcomes and eliminate health disparities.

Response:

N/A: This study does not utilize CBPR.

15.2 *Describe the composition and involvement of a community advisory board.*

Response:

N/A: This study does not have a community advisory board.

NOTE: One example includes: on-call availability of a counselor or psychologist for a study that screens subjects for depression.

Response: NA

16.4 Describe your process to ensure that all persons assisting with the research are adequately informed about the protocol, the research procedures, and their duties and functions.

Response: The PI will train and provide supervision to the Research Assistant who has completed the training on human subjects and ethics in research (CITI). During the initial meetings, the PI will provide handouts or files to inform the protocol, the research procedures, and RAs' duties and functions. There will be biweekly meetings among RAs and the PI to ensure all research members follow the research procedures.

17.0 Other Approvals

17.1 Describe any approvals that will be obtained prior to commencing the research (e.g., school, external site, funding agency, laboratory, radiation safety, or biosafety).

Response:

- N/A:** This study does not require any other approvals.

18.0 Provisions to Protect the Privacy Interests of Subjects

18.1 Describe how you will protect subjects' privacy interests during the course of this research.

NOTE: Privacy refers to an individual's right to control access to him or herself. Privacy applies to the person. Confidentiality refers to how data collected about individuals for the research will be protected by the researcher from release. Confidentiality applies to the data.

Examples of appropriate responses include: "participant only meets with a study coordinator in a classroom setting where no one can overhear", or "the participant is reminded that they are free to refuse to answer any questions that they do not feel comfortable answering."

Response: There will be no attempt to reveal participants' identities in any part of this study, and all data collected will not be shared with anyone except the research team members.

During the recruitment and interview phase, researchers will try to protect participants' privacy and confidentiality. When researchers are communicating with participants via phone or in person, communication will be occurring at a private place. In that way, other people will not overhear or witness research activities. When we advertise the study via social media, comments will be shut off to protect participants' confidentiality and privacy.

The data files, including audio files and participants' contact information will be shared using UB Box site, which only research members have access to. Data analysis will be performed and stored in the firewall,

encrypted, password protected computers provided by the School of Nursing. All computer databases and files will be maintained at the University at Buffalo. No data will be reported for individuals, and names of participants will not be identified in any reports on this study.

Pseudonyms and ID numbers will be used during the interview. The file links the pseudonyms and participants' names and contact information will be saved in the password protected file and this file will be only shared with the research team members as necessary during the recruitment phase.

During the interviews, researchers will explain that there are risks of breaches of confidentiality and privacy in spite of the effort to protect them. The participants can stop participating in the study at any point. Participants will be reminded that they are free to refuse to answer any questions that they do not feel comfortable answering.

18.2 Indicate how the research team is permitted to access any sources of information about the subjects.

*NOTE: Examples of appropriate responses include: school permission for review of records, consent of the subject, HIPAA waiver. This question **does apply** to records reviews.*

Response: We will obtain parental permission, consent, and assent of the subjects.

19.0 Data Management and Analysis*

19.1 Describe the data analysis plan, including any statistical procedures. This section applies to both quantitative and qualitative analysis.

Response: Quantitative data including demographic questions and survey questions will be analyzed with descriptive statistics. For the qualitative data from the interviews, a content analysis approach will be used with a deductive approach.

19.2 If applicable, provide a power analysis.

NOTE: This may not apply to certain types of studies, including chart/records reviews, survey studies, or observational studies. This question is asked to elicit whether the investigator has an adequate sample size to achieve the study objectives and justify a conclusion.

Response: No power analysis is needed.

19.3 Describe any procedures that will be used for quality control of collected data.

19.4 Response: data.

Response: Research team members will meet biweekly to check the research procedures and ensure the quality of the data.

20.0 Confidentiality*

A. Confidentiality of Study Data

Describe the local procedures for maintenance of confidentiality of study data and any records that will be reviewed for data collection.

20.1 A. *Where and how will all data and records be stored? Include information about: password protection, encryption, physical controls, authorization of access, and separation of identifiers and data, as applicable. Include physical (e.g. paper) and electronic files.*

Response: The data files will be stored in secure computers that are firewall and password protected. All paper documentation (including consent forms) will be stored in locked filing cabinets of the researchers' office and Center for Nursing Research office. The file containing participants' name and contact information, interview data (audio files and transcribed data), and consent forms will be stored in locked filing cabinets of the researchers' office and Center for Nursing Research office and/or saved as a password protected file in the PI's computer located in the PI's office at campus and the UB Box folder. All computer databases and files will be maintained at the University at Buffalo. No data will be reported for individuals, and names of participants will not be identified in any reports on this study. Pseudonyms and ID numbers will be used during the interview. The file links the pseudonyms and participants' names and contact information will be saved in the password protected file and this file will be only shared with the research team members as necessary during the recruitment phase.

The data files will be shared using UB Box site, which only research members have access to. Data analysis will be performed and stored in the firewall, encrypted, password protected computers provided by the School of Nursing.

20.2 A. *How long will the data be stored?*

Response: All files, including transcribed data, audio files, and links between the participants' identifying information will be deleted when the study is complete. Contact information for participants who want to be notified about future studies, their contact information will be stored for five years.

20.3 A. *Who will have access to the data?*

Response: Only the research members who are given permission.

20.4 A. *Who is responsible for receipt or transmission of the data?*

Response: The PI is responsible for the data receipt or transmission.

20.5 A. How will the data be transported?

Response: The data files without participants' names and contact information will be shared using UB Box site, which only research members have access to.

B. Confidentiality of Study Specimens

Describe the local procedures for maintenance of confidentiality of study specimens.

N/A: No specimens will be collected or analyzed in this research.
(Skip to Section 21.0)

20.6 B. Where and how will all specimens be stored? Include information about: physical controls, authorization of access, and labeling of specimens, as applicable.

Response: NA

